8.2 Sample Size

Enrollment of 60 subjects for this pilot study is based on the available patient population undergoing allogeneic HCT at the John Theurer Cancer Center (JTCC), expected rates of enrollment, and the historical data set from the past 3 years' allogeneic HCT experience at the JTCC, as well as the published literature from many centers performing allogeneic HCT for the same underlying diseases, and using similar preparative regimens. Statistical power of 60 subjects was considered adequate to detect fairly dramatic reductions of GVHD, as described in the Statistical Plan, below. Reductions of ~ 25% in grade II GVHD, and of ~ 62% in grade III-IV GVHD should be detected with 0.8 power, as discussed below. The similarly designed Maraviroc study [17] enrolled 38 patients, and reached statistical significance due to almost complete elimination of Grade III-IV GvHD. As we do not anticipate equally strong suppression of GVHD with telmisartan, we estimated that the somewhat larger number of 60 subjects would be appropriate to detect 60 -70% reduction. However, even a 20- 30% decrease in severe GVHD would have a real impact in the clinic, and this pilot study is not powered to detect this. Since grade II GVHD is more common, we are powered to detect a roughly 25% reduction in its

occurrence. This would be clinically beneficial, and would support further study of telmisartan for this indication.

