8.3 Statistical Analysis Plan

8.3.1 Efficacy Endpoints for Grade III-IV and Grade II GVHD.

The statistical test used for endpoints (Z test of proportions) takes the currently available 3 year JTCC data as the historical control data set for comparison. In reviewing these data, as currently available, it appears that the JTCC rates of severe GVHD, NRM, and cancer relapse are somewhat lower (i.e. better patient outcomes) than the national averages from published studies. For our final determinations of significance, we will use updated JTCC 3 year data as they become available at time of study completion.

Outcome variables examined include engraftment, GVHD, relapse, and NRM, however the efficacy hypotheses are constructed in relation to GVHD only.

Primary endpoint analysis

Historic GVHD data are available on 178 allogeneic transplants, of whom 46 (26%) experienced grade III or IV acute GVHD. All the other allogeneic transplantees (74%) had grade II GVHD. Based on these data, if 8 or fewer of the total 60 study participants experience grade III - IV acute GVHD during the course of the study, we will have demonstrated a protective effect for this criterion, with a $p < 0.05$, based on a one-way Z test for a decreased proportion.

Sample Size and Power Calculation Considerations

If we use the proportion $P=0.26$ as the rate of Grade III - IV GVHD in the current standard treatment, then using a one-sided exact test of the proportion and significance level of 0.05, testing if 9/60 (15%) rate of Grade III-IV GVHD is achievable with telmisartan treatment will have 58.8% power to detect this effect, if it exists. Testing for a 12% rate would achieve 82.2% power. Using the recommended level of significance, 0.025, for a one-sided test, testing if the grade III-IV GVHD by day 100 is 0.15, would have power of 44.4% of detecting this effect. At the 2.5 % level, testing if the rate is less than 0.11, will have 79.0 % power of detecting. Testing if the rate of grade III-IV in telmisartan treated transplantees is 0.10, will have 85.8% power of detecting this effect using the 2.5 % level of significance.

Numeric Results for testing $H_0: P = P_0$ versus $H_1: P < P_0$ using the PASS13 sample size software Test Statistic: Exact Test

Power	N	Proportion		Target Alpha	Actual Alpha	Beta	Reject H_0 If $R \leq$ This
		Given H_0 (P_0)	Given H_1 (P_1)				
0.8584	60	0.2600	0.1000	0.0250	0.0140	0.1416	8
0.7899	60	0.2600	0.1100	0.0250	0.0140	0.2101	8

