Incidence of Grade II GVHD

The historical data reported a rate of incidence of 74%. At 5% level of significance, a one-sided exact test of whether telmisartan can attain lower levels of 62% (37/60), would achieve 63.2 % power of detecting this if it is indeed efficacious. A lower incidence rate of 60% will be detected with 74.5% power.

Using the recommended level of significance, 0.025, a one-sided exact test of whether Telmisartan can attain the lower incidence rate of 62% will achieve a power of 52.8% to detect this effect. A one-sided exact test of whether the grade II GVHD incidence rate of 0.50 (30/60) can be attained by Telmisartan will have 97.4% power to detect this effect. A one-sided exact test of whether the incidence rate of 60% is possible with telmisartan will achieve power of 65.1% to detect it. A one-sided exact test of whether the grade II GVHD incidence rate of 0.57 can be attained by Telmisartan will have 80.5% power to detect this effect.

Numeric Results for testing $H_0: P = P_0$ versus $H_1: P < P_0$ using the PASS13 sample size software Test Statistic: Exact Test

Power	N	Proportion Given H0 (P0)	Proportion Given H1 (P1)	Target Alpha	Actual Alpha	Beta	Reject H0 if $R \leq$ This
0.9741	60	0.7400	0.5000	0.0250	0.0242	0.0259	37
0.8448	60	0.7400	0.5600	0.0250	0.0242	0.1552	37
0.8047	60	0.7400	0.5700	0.0250	0.0242	0.1953	37
0.7587	60	0.7400	0.5800	0.0250	0.0242	0.2413	37
0.6507	60	0.7400	0.6000	0.0250	0.0242	0.3493	37
0.5904	60	0.7400	0.6100	0.0250	0.0242	0.4096	37
0.5275	60	0.7400	0.6200	0.0250	0.0242	0.4725	37

Thus, with respect to grade 2 acute GVHD, if 37 or fewer patients of the 60 have grade 2 or lower acute GVHD, we will have demonstrated a drug effect at $p < 0.05$, using the one-way Z test of proportions.

To summarize, with only 26% of JTCC patients during the past 3 years exhibiting grade III or IV acute GVHD, we would have to see no more than 7 cases of grade III or IV acute GVHD (~ 12%) by the completion of the study to conclude that severe aGVHD had been reduced. However, with 74% of JTCC patients experiencing grade II aGVHD, we need only reduce that to 60%, or 36 of 60 patients having no more than grade II acute GVHD, in order to achieve significance.

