Monitoring Look	Number of Patients at Monitoring Look	Stop if Number of Toxicities is at least
1	9	2
2	21	3
3	33	4
4	45	5
5	58	6
6	60	7

The trial will be terminated if 2 or more patients out of the first 9 patients receiving experimental drug, Telmisartan, experience graft failure by day 100. If out of the first 21 patients, 3 or more have graft failure by day 100 then trial will be stopped. The boundaries were obtained such the Type I error, fixed at 1%, was spent over the multiple looks, hence the probability of stopping the trial prematurely by chance is 0.01.

Table 10. Operating characteristics for the stopping boundaries for Graft Failure Day 100

Probability Of Toxicity	Probability of crossing low bndry	Probability of stopping low bndry	Expected sample size low bndry	Probability of crossing high bndry	Probability of stopping high bndry	Expected sample size high bndry
0.07	0.373	0.373	46.1	0.365	0.365	46.2
0.08	0.477	0.477	42.4	0.467	0.466	42.5
0.09	0.576	0.576	38.7	0.565	0.565	38.8
0.10	0.666	0.666	35.0	0.655	0.654	35.1
0.11	0.744	0.744	31.6	0.734	0.733	31.7
0.12	0.809	0.809	28.5	0.799	0.798	28.6

Bndry, boundary.

From the operating characteristics, the probability of stopping the trial due to graft failure if the level of toxicity is at high level of 12% is 0.798. The expected sample size at termination of the trial is 28.6, if Telmisartan in fact more toxic than standard treatment.

Telmisartan Intolerance (includes angioedema and grade 3 or greater drug related adverse events after dose adjustments)

We use 5% as our acceptable rate of intolerance for drug treatment. Using repeated significance testing (Jennison and Turnbull) with 5.0% as lower proportion and 11.0% as higher proportion, 1% alpha level, and 80% power to for early termination, shape parameter of the boundary, delta=0.2, giving priority to the alternative hypothesis and continuous monitoring, the following stopping guidelines were computed by the *toxbdry* function in the Clinfun package in R 3.2.0.

Table 11. Stopping Boundaries for Intolerance to Telmisartan at Day 100

Monitoring Look	Number of Patients at Monitoring Look	Stop if Number of Toxicities is at least
1	8	2
2	22	3
3	38	4
4	55	5
5	60	6

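### The 0.8 efficacy power in 8.2 holds only if 60 patients are completed; at the plan's own expected safety rates, the 8.4 boundaries usually stop the trial first

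*Combined protocol and SAP*

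**What the plan says.** **Efficacy power.** Section 8.2 justifies 60 subjects partly by power, saying that reductions of about 25% in grade II "and of ~ 62% in grade III-IV GVHD should be detected with 0.8 power". Section 8.3.1 gives the basis: "If we use the proportion $P=0.26$ as the rate of Grade III - IV GVHD in the current standard treatment, then using a one-sided exact test". At one-sided 0.025 it adds: "Testing if the rate of grade III-IV in telmisartan treated transplantees is 0.10, will have 85.8% power of detecting this effect". The matching table rows are "0.8584 60 0.2600 0.1000 0.0250 0.0140 0.1416 8" and "0.7899 60 0.2600 0.1100 0.0250 0.0140 0.2101 8" (power, N, P0, P1, target alpha, actual alpha, beta, rejection limit). For grade II: "A one-sided exact test of whether the grade II GVHD incidence rate of 0.57 can be attained by Telmisartan will have 80.5% power". Neither section mentions early stopping, and every rejection limit is a count out of 60.

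**Safety stopping.** Section 8.4 sets boundaries for NRM, relapse, graft failure, intolerance and grade III-IV GVHD, in mandatory wording. For graft failure: "The trial will be terminated if 2 or more patients out of the first 9 patients receiving experimental drug". The text gives each rule a 1% type I error and combines the five as independent to 4.9%. Tables 6, 8, 10, 12 and 14 nevertheless print stopping probabilities of 0.335, 0.307, 0.365, 0.218 and 0.247 (high-boundary columns) at the lower, expected or acceptable, rates.

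**The concern.** The power statement describes a single-stage trial that always reaches 60. The trial as written is sequential: to succeed it must avoid all five boundaries and also have a low enough GVHD count at 60. With rules of 1% each the difference would be small. With rules that stop 22-37% of the time at the expected rates, it is large.

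The sample-size justification tells the sponsor and the IRB that a drug cutting severe GVHD by about 60% would be detected about 80% of the time. Under the printed rules, such a drug with no added toxicity would more often be stopped before its efficacy criterion could be applied. The plan also does not say what is then done with the GVHD data.

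**Working it through.** **1. The plan's powers reproduce.** A 62% reduction from 26% is 0.26 × 0.38 = 0.099, so the 10% row applies. With X ~ Binomial(60, p):
- P(X ≤ 8) = 0.8584 at p = 0.10, 0.7899 at p = 0.11, and 0.0140 at p = 0.26 (actual alpha).
- Grade II: P(X ≤ 37) = 0.8047 at p = 0.57.

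All match the document.

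**2. The stopping probabilities reproduce.** An exact patient-by-patient recursion on the printed boundaries (stop if the count reaches the limit at any n up to the listed n) gives these chances of not stopping before patient 60:

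| Rule | Assumed rate | Source of rate | Not stopped before 60 | Printed stopping probability |
|---|---|---|---|---|
| NRM | 15% | expected | 0.665 | 0.335 |
| Relapse | 12% | expected | 0.693 | 0.307 |
| Graft failure | 7% | expected | 0.635 | 0.365 |
| Intolerance | 5% | called acceptable, not historical | 0.782 | 0.218 |

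The GVHD rule hardly matters for an active drug. It is crossed with probability 0.0019 at 10% and 0.0028 at 11%, so P(not crossed and X ≤ 8) = 0.8577 and 0.7891.

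**3. Unconditional probability of success, rules independent (the plan's convention).**
- Reaching 60: 0.665 × 0.693 × 0.635 × 0.782 = 0.229.
- Grade III-IV at 10%: 0.229 × 0.8577 = 0.196.
- Grade III-IV at 11%: 0.229 × 0.7891 = 0.181.
- Grade II at 57%, leaving the GVHD rule aside: 0.229 × 0.8047 = 0.184.

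If a crossing at patient 60 itself also counts, completion is 0.226 and the grade III-IV figures are 0.194 and 0.179.

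**4. Sensitivity.** Rates other than those in step 2 are assumptions, except where a source is named.

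| Scenario | Reach 60 | Success (11% to 10% GVHD) |
|---|---|---|
| NRM and relapse mutually exclusive (simulation) | 0.22 | 0.17-0.19 |
| Latent correlation 0.5 (simulation) | 0.30 | 0.27-0.28 |
| Latent correlation 0.8 (simulation) | 0.38 | 0.36-0.37 |
| NRM 10% | 0.32 | 0.25-0.27 |
| Intolerance 0.5% (poor-tolerability figure in 10.2) | 0.29 | 0.23-0.25 |
| NRM 10%, intolerance 0.5% | 0.40 | 0.32-0.35 |
| NRM 10%, intolerance 0.5%, relapse 6% | 0.56 | 0.44-0.48 |
| NRM 10%, relapse 8%, graft failure 5%, intolerance 2% | 0.67 | 0.53-0.58 |
| Step 2 rates, only crossings by patient 44 block enrolment (outcome lag) | 0.29 | 0.23-0.25 |

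**5. A bound free of the dependence assumption.** Success requires that the graft-failure rule does not stop the trial. At a 7% rate with no outcome lag, success therefore cannot exceed 0.635 however the outcomes are related. That is 0.790 − 0.635 = 0.155 to 0.858 − 0.635 = 0.223 below the printed powers.

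**6. Cause.** If the four non-GVHD rules each had 1% error, completion would be 0.99⁴ = 0.961 and success 0.961 × 0.8584 = 0.825 or 0.961 × 0.7899 = 0.759. With the printed boundaries and all five outcomes at their lower rates, the chance of a stop is 1 − (0.665 × 0.693 × 0.635 × 0.782 × 0.753) = 0.83, against the stated 0.049.

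**The case against.** **The printed powers are not miscalculated.** This stands. They are labelled N=60, and quoting fixed-sample efficacy power without a discount for safety stops is common. The convention is harmless only when such stops are rare under acceptable safety, and the plan's own tables show that they are not.

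**It is a consequence of one defect in 8.4.** Largely true: boundaries that met the stated 1% would nearly restore the power. But if the sponsor only corrects the 1% label and keeps the boundaries, the claim in 8.2 remains unsupported.

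**The safety rates are pessimistic for an active drug.** This has force. NRM includes GVHD deaths (7.2.2), section 2.0 calls intestinal GVHD the main cause of early death, 7.2.4 calls early relapse rare, and 5% intolerance is an acceptable rate. Step 4 allows for these. No scenario there reaches 0.8.

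**An early stop need not forfeit efficacy.** A test of a proportion can be run at any n, and the plan does not forbid it. Applying the exact test at the stopped n, with step 2 rates and GVHD independent of stopping, gives 34-38% at one-sided 0.025 and 43-46% at 0.05. The plan specifies no such analysis, so the fair criticism is that reporting after a stop is undefined.

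**The DSMB only recommends** (9.4). The wording of 8.4 is nevertheless mandatory, and the power should describe the rules as written.

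A reader might infer that the trial's power simply is 18-20%, or that 63.5% is an absolute ceiling. The documents support neither. The first rests on independence, the step 2 rates and every early stop counting as failure. The second holds only at a 7% graft-failure rate without lag: that rule's ceiling is 0.679 if only crossings by patient 44 count, and 0.82 at a 5% rate.

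**Conclusion.** The concern holds in this form: the powers in 8.2 and 8.3.1 are correct for 60 completed patients, but 8.2 presents 0.8 as the power of a trial that its own safety rules would usually stop earlier at the rates the plan calls expected or acceptable. Under independence, unchanged safety rates and early stops scored as failure, the unconditional probability of success is about 18-20%. Correlation of 0.5-0.8 raises it to about 27-37%. NRM at 10% and intolerance at 0.5%, with relapse at 12% or 6%, raise it to about 32-48%. The exact value depends on assumptions the documents do not settle; the shortfall from 0.8 persists across every scenario examined. The source is the conflict between the stated 1% per rule and the 22-37% in the plan's tables.

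**What to change.** - In 8.2 and 8.3.1, label the PASS figures as conditional on completing 60 patients, and reword the 0.8 power sentence in 8.2 to match.
- Beside them, print the unconditional probability of success under the final boundaries, as a range, stating the assumptions on dependence between outcomes, safety rates and treatment of early stops.
- In 8.4, reconcile the 1% type I error text with the boundary and operating-characteristic tables. If the boundaries change, recompute the unconditional figure.
- State that if a boundary stops the trial before 60 patients, GVHD is reported as an estimate with an exact confidence interval and the 60-patient efficacy criterion is not applied.

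The cost is SAP wording and a short exact calculation, with no extra patients or procedures. The downside is that the stated power becomes less favourable, markedly so if the printed boundaries are kept.

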8.3 Statistical Analysis Plan

8.3.1 Efficacy Endpoints for Grade III-IV and Grade II GVHD.

The statistical test used for endpoints (Z test of proportions) takes the currently available 3 year JTCC data as the historical control data set for comparison. In reviewing these data, as currently available, it appears that the JTCC rates of severe GVHD, NRM, and cancer relapse are somewhat lower (i.e. better patient outcomes) than the national averages from published studies. For our final determinations of significance, we will use updated JTCC 3 year data as they become available at time of study completion.

Outcome variables examined include engraftment, GVHD, relapse, and NRM, however the efficacy hypotheses are constructed in relation to GVHD only.

Primary endpoint analysis

Historic GVHD data are available on 178 allogeneic transplants, of whom 46 (26%) experienced grade III or IV acute GVHD. All the other allogeneic transplantees (74%) had grade II GVHD. Based on these data, if 8 or fewer of the total 60 study participants experience grade III - IV acute GVHD during the course of the study, we will have demonstrated a protective effect for this criterion, with a $p < 0.05$, based on a one-way Z test for a decreased proportion.

Sample Size and Power Calculation Considerations

If we use the proportion $P=0.26$ as the rate of Grade III - IV GVHD in the current standard treatment, then using a one-sided exact test of the proportion and significance level of 0.05, testing if 9/60 (15%) rate of Grade III-IV GVHD is achievable with telmisartan treatment will have 58.8% power to detect this effect, if it exists. Testing for a 12% rate would achieve 82.2% power. Using the recommended level of significance, 0.025, for a one-sided test, testing if the grade III-IV GVHD by day 100 is 0.15, would have power of 44.4% of detecting this effect. At the 2.5 % level, testing if the rate is less than 0.11, will have 79.0 % power of detecting. Testing if the rate of grade III-IV in telmisartan treated transplantees is 0.10, will have 85.8% power of detecting this effect using the 2.5 % level of significance.

Numeric Results for testing $H_0: P = P_0$ versus $H_1: P < P_0$ using the PASS13 sample size software Test Statistic: Exact Test

Power	N	Proportion		Target Alpha	Actual Alpha	Beta	Reject H_0 If $R \leq$ This
		Given H_0 (P_0)	Given H_1 (P_1)				
0.8584	60	0.2600	0.1000	0.0250	0.0140	0.1416	8
0.7899	60	0.2600	0.1100	0.0250	0.0140	0.2101	8

Incidence of Grade II GVHD

The historical data reported a rate of incidence of 74%. At 5% level of significance, a one-sided exact test of whether telmisartan can attain lower levels of 62% (37/60), would achieve 63.2 % power of detecting this if it is indeed efficacious. A lower incidence rate of 60% will be detected with 74.5% power.

Using the recommended level of significance, 0.025, a one-sided exact test of whether Telmisartan can attain the lower incidence rate of 62% will achieve a power of 52.8% to detect this effect. A one-sided exact test of whether the grade II GVHD incidence rate of 0.50 (30/60) can be attained by Telmisartan will have 97.4% power to detect this effect. A one-sided exact test of whether the incidence rate of 60% is possible with telmisartan will achieve power of 65.1% to detect it. A one-sided exact test of whether the grade II GVHD incidence rate of 0.57 can be attained by Telmisartan will have 80.5% power to detect this effect.

Numeric Results for testing $H_0: P = P_0$ versus $H_1: P < P_0$ using the PASS13 sample size software Test Statistic: Exact Test

Power	N	Proportion Given H0 (P0)	Proportion Given H1 (P1)	Target Alpha	Actual Alpha	Beta	Reject H0 if $R \leq$ This
0.9741	60	0.7400	0.5000	0.0250	0.0242	0.0259	37
0.8448	60	0.7400	0.5600	0.0250	0.0242	0.1552	37
0.8047	60	0.7400	0.5700	0.0250	0.0242	0.1953	37
0.7587	60	0.7400	0.5800	0.0250	0.0242	0.2413	37
0.6507	60	0.7400	0.6000	0.0250	0.0242	0.3493	37
0.5904	60	0.7400	0.6100	0.0250	0.0242	0.4096	37
0.5275	60	0.7400	0.6200	0.0250	0.0242	0.4725	37

Thus, with respect to grade 2 acute GVHD, if 37 or fewer patients of the 60 have grade 2 or lower acute GVHD, we will have demonstrated a drug effect at $p < 0.05$, using the one-way Z test of proportions.

To summarize, with only 26% of JTCC patients during the past 3 years exhibiting grade III or IV acute GVHD, we would have to see no more than 7 cases of grade III or IV acute GVHD (~ 12%) by the completion of the study to conclude that severe aGVHD had been reduced. However, with 74% of JTCC patients experiencing grade II aGVHD, we need only reduce that to 60%, or 36 of 60 patients having no more than grade II acute GVHD, in order to achieve significance.

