4.1.1 Inclusion Criteria

Subjects must meet all of the following inclusion criteria to be eligible for enrollment into the study:

1. Meet the eligibility criteria for HCT as defined by the Standard Operating Procedures (SOP) of the blood and marrow transplantation program of Hackensack University Medical Center.

2. Diagnosis of:

- Acute myeloid or lymphoid leukemia in remission,
- Myelodysplastic syndrome,
- Chronic lymphoid leukemia,
- Non-Hodgkin lymphoma,
- Hodgkin lymphoma,
- Chronic myeloid leukemia in chronic or accelerated phase,
- Myeloproliferative disorder, or
- Multiple myeloma

3. Undergoing allogeneic HSC transplantation from a related or unrelated donor matched at least at 7 of 8 of the HLA-A, -B, -C, and DR loci (“8/8” or “7/8” match)

4. Planned to receive standard GvHD prophylaxis regimen. Subjects receiving rabbit ATG (Thymoglobulin) as part of their conditioning regimen are eligible to participate.

5. Male or female patient age 18 years or older

6. Karnofsky performance status $\geq 70\%$ at time of initiation of pre-transplant conditioning

7. Transplantation-specific co-morbidity score of <5 at time of initiation of pre-transplant conditioning

8. Patients taking antihypertensive medications (including telmisartan) are eligible but the patient must discontinue treatment at least 48 hours prior to first dose of study medication. In cases where the patient’s physicians feel it would be inadvisable to stop all anti-hypertensive treatment prior to starting telmisartan, the patient may continue on amlodipine, hydrochlorothiazide, furosemide, or other non-ARB, non-ACE inhibitors, or non-potassium sparing anti-hypertensives. If ARBs, ACE inhibitors, renin inhibitors, spironolactone, or other potassium sparing drugs cannot be discontinued prior to starting telmisartan, the patient will be ineligible for the study.

9. Capable of giving informed consent and having signed the informed consent form

4.1.2 Exclusion criteria:

Subjects who meet any of the following exclusion criteria will not be eligible for enrollment in this study:

1. Inability to provide informed consent

2. Subjects with known heart failure, advanced renal impairment requiring renal replacement therapy, or liver failure although these patients would most likely not be eligible for HCT, as per SOP of the blood and marrow transplantation program of Hackensack University Medical Center.

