5.0 STUDY DESIGN

5.1 Overall Study Design

This is multi-center, open-label, prospective study of telmisartan in addition to standard GvHD prophylaxis and treatment for the prevention of acute GVHD in approximately 60 subjects undergoing allogeneic HCT for treatment of a hematologic malignancy. The first 5 patients enrolled will receive telmisartan in an escalating dose according to the following schedule, with day 0 as the day of HCT: day -5 (40 mg), day -4 (80 mg), day -3 (80 mg), day -2 (160 mg), day -1 (160 mg). For these first five enrollees, telmisartan dose will be adjusted for grade 3 or 4 hypotension, as defined by CTCAEv4, as follows: the next day's dose will be one half the previously given dose (e.g. 20 vs. 40, or 40 vs. 80, or 80 vs. 160). If grade 3 or greater hypotension occurs at 20 mg, drug will be discontinued and the patient will be removed from the study. If the patient tolerates 40, or 80 mg, without hypotension, the dose will be increased to 80 or 160 mg, respectively, for the following day. If that (higher) next day's dose is tolerated, 160 mg will be given for the remainder of the trial as outlined below. From day 0 onward, any dose modifications will follow the dose adjustment algorithm outlined in section 5.3.4 below.

If two or more of the first five patients enrolled do not tolerate dose escalation to a stable daily dose of 160 mg by day 0, the trial will be paused, and the remaining volunteers will be enrolled following the same 5-day dose escalation procedure to establish a day 0-100 dose for each subject. All other study safety and endpoints, and dose adjustments will remain as described herein.

If four or more of the first five subjects tolerate 160 mg daily dosing by day 0, the remaining subjects enrolled will begin telmisartan on day -2 at 160 mg/day, as described below.

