5.3 Treatment Schedule

5.3.1 Standard GvHD Prophylaxis

All subjects will receive a standard GvHD prophylaxis regimen selected at the discretion of their transplant physician. The standard GvHD prophylaxis utilized at the study site includes:

- Tacrolimus 0.03 mg/kg/day by continuous infusion starting on day -2 pre-transplantation, adjusted as needed to achieve a serum level of 10-15 mcg/mL, and
- Methotrexate 5 mg/m² given IV on days +1, 3, 6, and 11 after transplantation.

While a tacrolimus/methotrexate-based regimen is used after a variety of transplant conditioning regimens and for a variety of diseases, alternate standard regimens may be used. The standard GvHD prophylaxis regimen is not dictated by this protocol. GvHD prophylaxis regimens utilizing an investigational agent (other than telmisartan) are prohibited.

5.3.2 Telmisartan Dosing and Discontinuation of Other Anti-Hypertensive Drugs.

The first five subjects enrolled will discontinue any anti-hypertensive medications they are taking at least 24 hours prior to beginning the telmisartan dose escalation on day -5. For subsequent enrollees, subjects will be asked to discontinue any antihypertensive medications they may be taking at least 48 hours prior to first dose of study medication.

For the purposes of this study, a commercial supply of Micardis brand (Boehringer Ingelheim) of telmisartan tablets will be used due to the superior release kinetics of Micardis compared to several generic brands [105], and to ensure uniformity of product during the trial. All subjects (other than the first 5 enrollees, discussed above) will receive 160 mg telmisartan p.o. once daily starting two days prior to HCT (Day -2) and continuing for 101 days (until Day +98 post-HCT), unless discontinued early from treatment. Subjects will be instructed to take their study medication at approximately the same time every day, before bedtime, or upon waking, but there are no strict requirements for the timing of administration. Downward dosing adjustments will be made according to the steps outlined in section 5.3.4.

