8.0 STATISTICAL CONSIDERATIONS

8.1 Data Management

Data pertaining to the subject's medical history, HCT course and outcome, and clinical follow-up will be abstracted from multiple sources including medical records (paper and electronic records in EPIC), the Tumor Registry at HackensackUMC, and the HCT database maintained by the Blood and Marrow Transplantation Program at the John Theurer Cancer Center. Any study required data not available from an existing source will be recorded on study specific source document worksheets. All data will be entered into a study specific, password-protected database accessible only by qualified members of the research team. Periodic audits of study data will be performed in conjunction with Corporate Compliance at HackensackUMC. Coded data from exploratory studies will be recorded in laboratory notebooks prior to inclusion in the study database.

All subjects will be assigned a study specific identification number (ID#). All study data will be recorded using the subject's ID#. A key linking ID#'s with subject identities, accessible only by qualified members of the research team, will be kept separate from study data.

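### The efficacy test in 8.3.1 compares 60 selected patients with 178 historical transplants and states no eligibility filter, matching or adjustment, so its 1.4% error rate holds only if the enrolled patients' standard-care risk is 26%

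*Combined protocol and SAP*

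**What the plan says.** Section 8.3.1 sets the method: "The statistical test used for endpoints (Z test of proportions) takes the currently available 3 year JTCC data as the historical control data set". The comparator is described in two sentences: "Historic GVHD data are available on 178 allogeneic transplants, of whom 46 (26%) experienced grade III or IV acute GVHD", and "All the other allogeneic transplantees (74%) had grade II GVHD". A protective effect is declared "if 8 or fewer of the total 60 study participants experience grade III - IV acute GVHD during the course of the study". The closing summary of the same section gives a different limit, no more than 7 cases. The JTCC figures are to be updated at study completion. Neither the test nor the update mentions eligibility, matching, weighting or covariates. Regression appears only in 8.3.2, for exploratory markers within the trial.

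Trial patients are selected. Section 4.1.1 requires at least a 7/8 HLA match, Karnofsky of 70% or more, a co-morbidity score below 5 and, for acute leukemia, remission. Section 5.5.2 counts as evaluable only those still on telmisartan through day +14 and replaces those who stop earlier.

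Other factors are left open. Donors may be related or unrelated. On ATG, 4.1.1 says "Subjects receiving rabbit ATG (Thymoglobulin) as part of their conditioning regimen are eligible to participate". On prophylaxis, 5.3.1 says "alternate standard regimens may be used".

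Section 5.1 opens with "This is multi-center, open-label, prospective study of telmisartan", while eligibility (4.1.1), recruitment (4.2.1), follow-up visits (5.3.3), sample size (8.2) and ethics review (11.4) refer only to Hackensack or its cancer center.

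**The concern.** In a single-arm trial the comparator does the work that randomisation would otherwise do. If the 60 evaluable patients would have had less severe GVHD than the 178 even without telmisartan, the crude test credits the difference to the drug. If they would have had more, a real effect can be missed.

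The documents show concrete routes to such a difference: entry restrictions and a day +14 requirement for trial patients, with no counterpart stated for the controls. They also leave free several background factors that could plausibly affect GVHD. Updating the JTCC data changes the calendar window but not the case mix. Since 8.3.1 treats a count at or below the limit as a demonstrated effect, the error rate attached to that statement matters.

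**Working it through.** **Inputs.** n = 60; historical rate 46/178 = 0.258, used as P0 = 0.26; rejection limit R ≤ 8 (8.3.1 and its power table); alternative limit R ≤ 7 (closing summary of 8.3.1).

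**Formula.** With X ~ Binomial(60, p), the chance of declared success is P(X ≤ R). Under an inert drug, p is the enrolled patients' standard-care risk.

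**Reproducing the plan, R ≤ 8.**
- p = 0.26: 0.0140 (stated actual alpha 0.0140).
- p = 0.10: 0.8584 (stated power 0.8584).
- p = 0.11: 0.7899 (stated power 0.7899).

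The plan's arithmetic is right for a fixed, comparable 26%.

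**Inert drug, other standard-care risks.** The risks below 26% are assumptions, because the documents give no rate by donor type, match, ATG, prophylaxis or eligibility status.

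| Standard-care risk | P(X ≤ 8) | P(X ≤ 7) |
|---|---|---|
| 26% | 1.4% | 0.6% |
| 24% | 3.2% | 1.4% |
| 22% | 6.6% | 3.1% |
| 20% | 12.7% | 6.7% |
| 18% | 22.4% | 13.1% |

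Under the ≤8 rule, false success passes 2.5% once the risk is below 24.6% and 5% once it is below 22.8%. Under the ≤7 rule the same points are 22.6% and 20.8%.

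**Shift the other way.** Keep the relative effect of the 10% alternative: 0.10/0.26 = 0.385. At an assumed standard-care risk of 30%, the treated rate is 0.30 × 0.385 = 0.1154, and P(X ≤ 8) = 0.748, against 0.858 as planned. An inert drug then succeeds with probability 0.2%.

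**Effect of a corrected null.** If standardising to the enrolled mix gave a null of 22%, the exact one-sided 2.5% limit would be R ≤ 6 (P = 0.0131 at 22%), and power at a true 10% would be 0.606. At a 20% null the limit is R ≤ 5 (P = 0.0121) and power is 0.437.

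**Comparator definition.** 178 − 46 = 132, and 132/178 = 74%. Since 26% + 74% = 100%, the series as described contains nobody with grade 0 or I. Either it is limited to patients with grade II or worse, or the 74% means something else. Any adjusted model fitted to it would inherit that ambiguity.

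**The case against.** The strongest reply is that open is not the same as different. No section says that donor type, ATG or prophylaxis was distributed differently among the controls, the named site is the same, and the window is updated. That stands: no actual shift can be shown, and the lower risks above are assumptions. It does not remove the point, because the eligibility restrictions and the day +14 requirement are documented for the trial and nothing equivalent is stated for the controls.

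A second reply is that 1.4% is a flattering benchmark when 8.3.1 claims only p < 0.05. That also stands in part. At 22% the ≤8 rule gives 6.6%, only modestly above 5%, and the ≤7 rule stays below 5%.

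Third, section 8.2 calls this a pilot meant to support further study. That makes a historical comparison acceptable, but 8.3.1 still words the result as a demonstrated effect.

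Two stronger readings are tempting. A reader might infer that the 178 are an unselected, all-comer series; the text states no filter but does not say that, and the absence of grade 0-I patients sits badly with it. A reader might also infer from the word multi-center that other centres could produce a false success. The rest of the protocol points to Hackensack only, and 8.3.1 says JTCC severe GVHD is somewhat below national averages, so other centres would tend to make success harder. If, as an illustration, 20 of 60 patients came from a centre at 35% and 40 from one at 26%, an inert drug would meet ≤8/60 with probability 0.35%.

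**Conclusion.** The concern holds as a weakness of the comparison, not as evidence that the result will be wrong. The planned test has its stated 1.4% error only at a standard-care risk of 26% in the evaluable patients, and nothing in the documents establishes or checks that. Over an assumed range of 24% to 18%, false success runs from 3.2% to 22.4% under the ≤8 rule and from 1.4% to 13.1% under the ≤7 rule. At 30%, power for the planned relative reduction drops to about 75%. It would go too far to say that case mix makes a false success likely: 50% would need a standard-care risk near 14%, and the shift may run in either direction. Restricting and adjusting the comparison is a cheap improvement to the trial's only efficacy conclusion. It removes measured differences; unmeasured ones remain.

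**What to change.** 1. Define the historical set in 8.3.1: dates, inclusion rules, how grades were assigned, and why 26% and 74% leave no grade 0-I patients.
2. Restrict it to JTCC patients who would have met the criteria in 4.1, with a day +14 landmark matched as closely as possible to 5.5.2. Controls cannot stop a drug they never took, so state what the landmark means for them.
3. Prespecify, before outcomes are compared, an analysis adjusted for a few baseline factors: donor type, HLA match, ATG, conditioning and prophylaxis. A pooled Firth logistic model with a telmisartan term would do. So would observed against expected counts, provided the uncertainty in the expected count is carried through. Report the crude test beside it, with one success limit.
4. Reconcile multi-center in 5.1 with the Hackensack-only text. If another site enrols, limit this comparison to JTCC patients.

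**Cost.** Records must be extracted for up to 178 controls. Section 8.1 names "the HCT database maintained by the Blood and Marrow Transplantation Program at the John Theurer Cancer Center" as a data source, but whether it holds these fields for the controls must be confirmed. Restriction leaves fewer than 178 controls and possibly fewer than 46 events, so perhaps fewer covariates and some loss of precision. If the enrolled mix proves lower risk, honest power falls, for example to 61% against a 22% null for a true rate of 10%. No added patients, visits or changes in treatment are needed.
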